**Statistical Analysis Plan**  
 Sponsor: Selecta Biosciences  
 Protocol No.: SEL-212/302

---

datasets will be combined in the same way as the multiple imputation analysis, but the response probabilities will be pre-specified as opposed to generated from a logistic regression.

An  $11 \times 11$  table will be displayed for each SEL-212 active arm vs. placebo comparison where the p-values from the tipping point analysis under each combination of underlying response probabilities for those with missing data are shown.

A table with number and type/reason of missing values in the primary efficacy variable will be provided by treatment group on the ITT population for each estimand.

Frequency table of the treatment responders considering the responder definition in Section 9.1 but also the definitions in Section 6 for the estimands of interest will be provided by treatment group for all three estimands defined in Section 6, and the difference in proportions between each SEL-212 treatment group and placebo will be presented together with 97.5% confidence intervals. The treatment effect odds ratio and 97.5% confidence intervals will be presented from the logistic regression.

### 9.3. Key Secondary Efficacy Estimands and Analyses

#### 9.3.1. Hierarchical Testing Approach of Key Secondary Efficacy Estimands

If the superiority of both(one) SEL-212 treatment group(s) against placebo for the main estimand of the primary efficacy is shown with a p-value  $\leq 0.025$ , the hierarchical testing approach will continue to the testing of the main estimands of the key secondary efficacy comparing pairwise both (one) SEL-212 treatments against placebo. Only the main estimands of the key secondary efficacy will be tested in the successive order as defined in Section 6.2. The test result of the  $n^{\text{th}}$  key secondary efficacy estimand will be considered as confirmatory, if the p-value of the two-sided test of the previous estimand resulted in a value less or equal 0.025.

#### 9.3.2. Key Secondary Efficacy Analyses

##### 9.3.2.1. *Reduction of mean sUA as computed by subtracting the Baseline sUA level from the mean sUA during Treatment Period 6*

Both estimands, as well as the estimands where the ITT is replaced by each mITT, all randomized and PP sets, for this key secondary efficacy will be tested between each SEL-212 treatment group versus placebo using an ANCOVA, with reduction of mean sUA at TP6 from baseline as the dependent variable, treatment and randomization stratum as fixed effects, and baseline sUA value as covariates. Missing values of change from baseline will be multiple imputed by using the RPMM method considering tophus status at baseline and treatment group. The Least Square (LS) Mean difference between each SEL-212 and placebo treatments groups will be estimated along with its 97.5% confidence interval, and 2-sided p-values.

The change from baseline in mean sUA across TP6 will be summarized by treatment group on the ITT, the defined mITT populations, all randomized and the PP population.

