8.3.3 Enrolled Patient Withdrawal and Discontinuations

8.3.3.1 Withdrawal Procedures

Early termination from the study occurs when an enrolled patient withdraws consent or is lost to follow-up. The reason for withdrawal will be evaluated and recorded in the case report form (CRF) and source documents.

Patients may withdraw consent at any time. Reason(s) for withdrawal of consent, failure to return for the necessary visits, or termination from the study should be documented. All patients that withdraw early upon termination should have the Early Termination visit assessments completed (i.e., End of Study assessments) ([Appendix A](#)), if the assessments pose no risk to the patient and the patient allows such assessments.

 Selecta Biosciences	PHASE 3 STUDY: SEL-212/302 VERSION: 7.1	EFFECTIVE DATE 15 DEC 2022
---	--	-------------------------------

The Investigator should consult with the Sponsor/medical monitor prior to withdrawing study drug from any patient in the study. Since this is a multiple-dose study, once dosed, patients generally should not be terminated by the Investigator. The patient should be followed through the end of Treatment Period 6, unless the patient withdraws consent or is lost to follow-up. In situations where continued participation in certain aspects of the study pose a risk to the patient, with consultation with the medical monitor, the Investigator should discontinue those procedures that pose a risk and should continue to collect data and conduct those assessments that do not put the patient at risk through the end of Treatment Period 6. Patients with compliance issues or major deviations that effect data quality will also continue to be followed through the end of Treatment Period 6 collecting as much data on the patient as possible, unless otherwise indicated by the Sponsor.

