**Stopping Rules:**

A patient will be withdrawn from study drug for meeting the following stopping rule:

- sUA level < 2.0 mg/dL, measured 1 hour after the infusion of the second component of study drug is completed during Treatment Period 1

AND

- sUA level > 1.0 mg/dL measured at the Day 21 visit of Treatment Period 1 or sUA level > 6.0 mg/dL at the Day 21 visit of Treatment Periods 2, 3, 4, or 5

Stopping rules will be assessed by an independent, central, unblinded medical monitor.

If withdrawn from study drug, the patient will continue study visits to the end of Treatment Period 6. The window for all Day 21 visits is +2/-1 days.

If a Day 21 visit sUA value drawn within the protocol window is not available, but if a sUA value drawn at an unscheduled visit after the Day 21 window is available prior to dosing that is  $\leq$  1.0 mg/dL during Treatment Period 1 or  $\leq$  6.0 mg/dL during Treatment Periods 2, 3, 4, or 5, the patient will not be required to be withdrawn from study drug and will be eligible to receive their subsequent dose.

If 1) a Day 21 visit sUA value drawn within the protocol window is not available and no subsequent sUA results are available or 2) a Day 21 visit sUA value drawn within the protocol window is not available and a subsequent sUA drawn at an unscheduled visit after the Day 21 window is  $>$  1.0 mg/dL during Treatment Period 1 or  $>$  6.0 mg/dL during Treatment Periods 2, 3, 4, or 5, then the patient will be withdrawn from study drug based on the protocol deviation. If a protocol deviation occurs where a patient is not able to be dosed within the dosing day window (for example in the case of COVID-19 restrictions temporarily preventing dosing) the current treatment period will be extended up to a maximum of 90 days without skipping doses

This document is confidential.

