## 6.2. Estimands for Key Secondary Efficacy

### 6.2.1. Estimands for 'Reduction of mean sUA as computed by subtracting the Baseline sUA level from the mean sUA during Treatment Period 6'

The main estimand for the key secondary efficacy endpoint 'Reduction of mean sUA as computed by subtracting the Baseline sUA level from the mean sUA during Treatment Period 6' is defined as follows:

- Population: Of all patients with gout refractory to conventional treatment defined by the study inclusion / exclusion criteria, the analysis population will include patients who were randomized to study treatment and who were dosed (ITT population)
- Variable: Continuous variable showing the difference between the mean sUA value recorded in TP6 and the baseline sUA value for each individual.
- Population-level summary: Difference in LS means between each SEL-212 treatment group vs. placebo.
- Intercurrent events:
  - o All intercurrent events (as listed in 6.1 for the primary estimand) except deaths will be considered using the treatment policy strategy
  - o For deaths the last available value will be used (while-on-treatment strategy), i.e. the baseline sUA value will be subtracted from mean sUA values across the most recently attended TP.

A second estimand for this key secondary endpoint will be defined similarly to the main estimand but with using the while-on-treatment strategy for all intercurrent events (as listed in 6.1 for the primary estimand).

The main and second estimands will be repeated five times, once with the population changed to each of the three defined mITT populations, once with the population changed to the all randomized set, and once with the population changed to the PP set.

This document is confidential.

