**Statistical Analysis Plan**  
 Sponsor: Selecta Biosciences  
 Protocol No.: SEL-212/302

---

treatment and randomization stratum as fixed effects, and baseline sUA value as covariates. Missing values of % change from baseline will be multiple imputed by using the RPMM method considering tophus status at baseline and treatment group. The Least Square (LS) Mean difference between each SEL-212 and placebo treatments groups will be estimated along with its 97.5% confidence interval, and 2-sided p-values.

However, residuals from this model will be checked for conformity to normality assumptions. Differences from normality in these residuals will result in the dependent variable being log-transformed and the ANCOVA applied to this outcome, adjusting for the same covariates. This model will then be considered the primary analysis for this estimand.

The percentage change from baseline in mean sUA across TP6 will be summarized by treatment group on the ITT, the defined mITT populations, the all randomized and the PP population.

**9.3.2.3. *The change from Baseline to Day 28 of Treatment Period 6 in the physical summary score of the Short Form Health Survey 36 (SF-36)***

Both estimands, as well as the estimands where the ITT is replaced by each mITT, all randomized and PP sets, for this key secondary efficacy endpoint will be tested between each SEL-212 treatment group versus placebo using MMRM with change in SF-36 summary score as dependent variable and treatment, period, treatment-by-period interaction, randomization stratum and baseline value of SF-36 summary score as fixed effect variables. The unstructured covariance structure will be used for the MMRM. The LSMean difference between each SEL-212 and placebo treatments groups will be estimated on the treatment-by-period interaction at TP6-Day 28 visit, along with its 97.5% confidence interval, and 2-sided p-values.

A sensitivity analysis will be performed for the main estimand: missing values of SF-36 summary score at TP6-D28 will be multiple imputed by using the RPMM method considering tophus status at baseline and treatment group, and the change from baseline to Day 28 of TP6 in SF-36 summary score will be analyzed using an ANCOVA with treatment and randomization stratum as fixed effects and the baseline value of SF-36 summary score as covariate.

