Both estimands, as well as the estimands where the ITT is replaced by each mITT, all randomized and PP sets, for this key secondary endpoint will be analysed in the same way as the primary endpoint, except a Chi-square test with continuity correction will be performed, given only patients with tophus at baseline will be included in the analysis. In addition, the logistic model used to carry out multiple imputation for missing response evaluation data in TP6 will only include the treatment group in the model (and not tophus status at baseline), as only patients with tophus at baseline will be included in the analysis.

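### The imputation model for the two sUA key secondaries omits baseline sUA and TP6 drug status, which can overstate the SEL-212 reduction by about 5 to 9% at the planned 8% early termination

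*SAP*

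**What the plan says.** SAP 9.3.2.1 (reduction of mean sUA) states: "Missing values of change from baseline will be multiple imputed by using the RPMM method considering tophus status at baseline and treatment group". SAP 9.3.2.2 (percent reduction) repeats it: "Missing values of % change from baseline will be multiple imputed by using the RPMM method considering tophus status at baseline and treatment group". SAP 7.3 only points to Section 9, and Protocol 13.4.2 says only that missing values are multiply imputed. The list of two predictors reads as complete: for the tophus-subset responder endpoint, SAP 9.3.2.5 says that its imputation model "will only include the treatment group in the model (and not tophus status at baseline").

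The analysis model is wider. The ANCOVA has "treatment and randomization stratum as fixed effects, and baseline sUA value as covariates".

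The main estimand (SAP 6.2.1, and 6.2.2 likewise) reads: "All intercurrent events (as listed in 6.1 for the primary estimand) except deaths will be considered using the treatment policy strategy". Off-drug values are therefore part of the target. On follow-up, SAP 3.3 says: "If withdrawn from study drug, the patient will continue study visits to the end of Treatment Period 6". Protocol 8.3.3.1 defines who leaves: "Early termination from the study occurs when an enrolled patient withdraws consent or is lost to follow-up".

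The tipping-point analysis in SAP 9.2 is specified for the primary endpoint. SAP 9.3.2.1 and 9.3.2.2 specify no sensitivity analysis for missing data.

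**The concern.** Under the stopping rule the SEL-212 arms should split by TP6 into patients still on drug with low sUA and patients withdrawn from drug with sUA nearer baseline. A treatment-policy estimand needs a plausible off-drug value for a missing off-drug patient. An imputation model that does not know drug status cannot supply one.

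Missingness and drug status are plausibly linked, because a patient who leaves the study before the TP6 dose cannot be on drug in TP6. The error would not cancel against placebo, where stopping saline should change sUA little. At stake is the size of the reported sUA reduction, and its interval, for the first two endpoints in the key secondary hierarchy.

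**Working it through.** **The plan's own figures.** The imputation sections give no number. Two planning inputs come from SAP 3.5: 45% SEL-212 responders, used here as a proxy for the share on drug in TP6, and about 8% early termination, used as a proxy for a missing TP6 value. The sample size built on them reproduces. For 45% versus 5%, two-sided 2.5%, 90% power and continuity correction, the result is 32 per arm, and 32/0.92 = 34.8, so 35.

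**What the imputation does.** With two categorical predictors, everyone in an arm-by-tophus cell has the same predicted mean. Predictive mean matching then becomes a near-random draw from the observed patients in that cell, whatever their drug status.

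**Size.** Let *p* be the share on drug in TP6, *m* the share missing, *f* the share of missing patients who are off drug, *a* the on-drug change and *c* the off-drug change.

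- True arm mean: T = p·a + (1 − p)·c
- On-drug share among donors: q = [p − m(1 − f)] / (1 − m)
- Arm mean after imputation: M = q·a + (1 − q)·c

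Take p = 0.45 and m = 0.08 (SAP 3.5). The values a = −7 mg/dL, c and f are assumptions.

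| f | c | q | T | M | Excess |
|---|---|---|---|---|---|
| 100% | 0 | 0.45/0.92 = 0.489 | −3.15 | −3.42 | 0.27 (9%) |
| 80% | 0 | 0.434/0.92 = 0.472 | −3.15 | −3.30 | 0.15 (5%) |
| 100% | −1.5 | 0.489 | −3.98 | −4.19 | 0.22 (5%) |
| 55% | 0 | 0.414/0.92 = 0.450 | −3.15 | −3.15 | 0 |

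The last row is missingness unrelated to drug status, since 1 − p = 55%. If the two milder assumptions are combined (f = 80%, c = −1.5), the excess is (0.472 − 0.45) × 5.5 = 0.12 mg/dL, or 3% of 3.98.

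When c = 0 and f = 100% the relative excess is m/(1 − m), whatever *a* and *p* are. With a = −5 the arm mean moves from −2.25 to −2.45, again 9%. If 15% were missing, which is an assumption above the planned figure, it would be 0.15/0.85 = 18%.

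**Simulation of the full procedure.** The settings were 300 runs, 47 per arm, 10 imputations, matching on 5 donors, and ANCOVA on treatment, tophus status and baseline sUA. Assumed values were baseline about 8.5 mg/dL (SD 1.2, floor 7), on-drug TP6 mean about 1 mg/dL, off-drug sUA near baseline, 60% with tophi, 75% of placebo on drug in TP6, and all missing patients off drug. At 8% missing, the difference from placebo was −3.25 on full data and −3.54 under the SAP model, an excess of 0.29/3.25 = 9%. About 49% of the values imputed in the active arm came from on-drug patients.

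**Test decision.** Simulated power was at least 99.7% in every scenario, for 8 to 25% missing and 45% or 37% on drug.

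**Which predictors repair it.** A second set of simulations at 8% missing, with an off-drug change of 0, gave −3.36 on full data and −3.67 under the SAP model. A model adding baseline sUA, last on-study sUA and drug status gave −3.36 when off-drug patients' last sUA had already risen. If the missing patients had left while still controlled, separate runs of that kind of model gave −3.57 and −3.88, so the result is sensitive to how drug status enters the model. Baseline sUA with drug status by treatment, without earlier sUA, returned −3.36 in every case run.

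**The case against.** The strongest reply has five parts.

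1. *Donors are mixed.* A reader might infer that missing off-drug patients simply receive responders' values. The documents do not support that. Patients withdrawn from drug stay in visits to the end of TP6, so off-drug donors exist and supply about half the draws. This stands, and the sizes above already allow for it.
2. *Missingness is limited.* SAP 9.1 uses unscheduled samples, samples after Day 28 and truncated curves. It sets the TP6 response to missing only when two or fewer assessments span less than 7 days. This stands as a reason not to assume much more than the planned 8%.
3. *The off-drug change may not be zero.* Protocol 7.4.1.1 allows a return to urate-lowering therapy 60 days after the last dose, while Protocol 9.2.1 and 10.5 bar it during participation. Those passages must be reconciled. If such therapy is used, the on/off gap narrows, as in the −1.5 mg/dL row. This stands.
4. *No decision changes.* A reader might infer that the hierarchy is at risk. With power near 100% in every scenario, it is not.
5. *Baseline sUA is balanced by randomization.* Omitting it should move the treatment contrast little unless missingness depends on it. The mismatch with the ANCOVA is real, but no bias from it has been quantified.

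A reader might also extend the point to SF-36, tender joints and HAQ-DI. There the SAP's main analysis is an MMRM that uses baseline and earlier visits, and the matching imputation is only a sensitivity analysis. The documents do not support the same concern about the main results for those endpoints.

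**Conclusion.** The concern holds in a limited form. For the two sUA key secondaries, the imputation ignores the variable that most separates TP6 values under a treatment-policy estimand, and no missing-data sensitivity analysis for these endpoints would expose the effect. At 8% missing the SEL-212 reduction is overstated by about 0.15 to 0.27 mg/dL, or 5 to 9%. That assumes 45% on drug, an on-drug change of −7 mg/dL, and either 80 to 100% of missing patients off drug with no off-drug change, or all off drug with an off-drug change of −1.5 mg/dL. Milder assumptions give less, and the bias vanishes if missing and observed patients are off drug equally often. The mg/dL values and the off-drug share among missing patients are assumptions, not figures from the documents. The estimate and its confidence interval are affected. The test decision is not.

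**What to change.** In SAP 9.3.2.1 and 9.3.2.2:

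- Impute within treatment arm, or include a treatment-by-drug-status interaction, using stratum, baseline sUA and on/off-drug status in TP6. Off-drug missing patients are then matched to off-drug patients who were followed through TP6.
- Use earlier on-study sUA only within drug-status groups. Otherwise a low last on-drug value can match a departed patient to on-drug responders and leave the bias in place or enlarge it.
- Add a delta-adjusted or tipping-point sensitivity analysis for these two endpoints.

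The cost is SAP wording and programming, because all the variables are already collected. The drawback is small off-drug donor cells. Placebo is the likeliest problem, since the stopping rule requires sUA below 2.0 mg/dL one hour after the first dose and few placebo patients should meet it. Strata may need pooling there, and the confidence interval may be slightly wider.

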##### 9.3.2.2. *Percent reduction of mean sUA as computed by subtracting the Baseline sUA level from the mean sUA during Treatment Period 6*

Both estimands, as well as the estimands where the ITT is replaced by each mITT, all randomized and PP sets for this key secondary efficacy will be tested between each SEL-212 treatment group versus placebo using an ANCOVA, with percentage change of mean sUA at TP6 from baseline as the dependent variable,

This document is confidential.

**Statistical Analysis Plan**  
 Sponsor: Selecta Biosciences  
 Protocol No.: SEL-212/302

---

treatment and randomization stratum as fixed effects, and baseline sUA value as covariates. Missing values of % change from baseline will be multiple imputed by using the RPMM method considering tophus status at baseline and treatment group. The Least Square (LS) Mean difference between each SEL-212 and placebo treatments groups will be estimated along with its 97.5% confidence interval, and 2-sided p-values.

However, residuals from this model will be checked for conformity to normality assumptions. Differences from normality in these residuals will result in the dependent variable being log-transformed and the ANCOVA applied to this outcome, adjusting for the same covariates. This model will then be considered the primary analysis for this estimand.

The percentage change from baseline in mean sUA across TP6 will be summarized by treatment group on the ITT, the defined mITT populations, the all randomized and the PP population.

**9.3.2.3. *The change from Baseline to Day 28 of Treatment Period 6 in the physical summary score of the Short Form Health Survey 36 (SF-36)***

Both estimands, as well as the estimands where the ITT is replaced by each mITT, all randomized and PP sets, for this key secondary efficacy endpoint will be tested between each SEL-212 treatment group versus placebo using MMRM with change in SF-36 summary score as dependent variable and treatment, period, treatment-by-period interaction, randomization stratum and baseline value of SF-36 summary score as fixed effect variables. The unstructured covariance structure will be used for the MMRM. The LSMean difference between each SEL-212 and placebo treatments groups will be estimated on the treatment-by-period interaction at TP6-Day 28 visit, along with its 97.5% confidence interval, and 2-sided p-values.

A sensitivity analysis will be performed for the main estimand: missing values of SF-36 summary score at TP6-D28 will be multiple imputed by using the RPMM method considering tophus status at baseline and treatment group, and the change from baseline to Day 28 of TP6 in SF-36 summary score will be analyzed using an ANCOVA with treatment and randomization stratum as fixed effects and the baseline value of SF-36 summary score as covariate.

The SF-36 summary score at scheduled visits and the change from baseline will be summarized by treatment group and period, on the ITT, the defined mITT populations, all randomized population and the PP population.

The SF-36 is a 36-item scale constructed to survey health status and quality of life ([Ware 1992](#)). The SF-36 assesses 8 health concepts: limitations in physical activities because of health problems; limitations in social activities because of physical or emotional problems; limitations in usual role activities because of physical health problems; bodily pain; general mental health (psychological distress and well-being); limitations in usual role activities because of emotional problems; vitality (energy and fatigue); and general health perceptions. The standard form of the instruments asks for patients to reply to questions according to how they have felt over the previous week.

The SF-36 consists of 8 scaled domain scores with range 0-100 with higher score indicating better health and 2 component scores (physical component and mental component). The 8 domains are:

- Vitality
- Physical functioning
- Bodily Pain
- General Health Perceptions

This document is confidential.

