The main estimand for the key secondary efficacy endpoint 'gout flare incidence in Treatment Period 1 to Treatment Period 6' and 'gout flare incidence in Treatment Period 1 to Treatment Period 3' considers as variable of interest 'Incidence of gout flare during the whole treatment period from start of treatment until end of month 6'. and 'incidence of gout flare during the first 3 months of treatment'. Gout flare incidence is defined as the total number of gout flares a patient experiences in respective time period divided by the length of observation of the patient in this time period. The handling of all intercurrent events except death will be according to the treatment-policy strategy. For deaths, the while-on-treatment strategy will be used. The population-level summary is the difference in the gout flare incidences between each SEL-212 treatment group versus placebo for the whole treatment period (start of treatment until end of month 6) and for the first 3 months of treatment. The analysis will be performed separately for the whole treatment (Treatment Period 1 to Treatment Period 6) and for the first 3 months (Treatment Period 1 to Treatment Period 3). whereby the confirmatory statistical comparison will be performed first for the whole treatment, then for the first 3 months.

Further estimands for the key secondary efficacy will be defined in the SAP.

For the above defined estimands, the key secondary efficacy endpoints which are numbered 1, 2, 8 and 9 will be tested between each SEL-212 treatment group versus placebo using an ANCOVA, adjusting for treatment, randomization stratum and baseline value of the respective variable. The Least Square (LS) Mean difference between each SEL-212 and placebo treatments groups will be estimated along with its 97.5% confidence interval, and 2-sided p-values.

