**Statistical Analysis Plan**  
 Sponsor: Selecta Biosciences  
 Protocol No.: SEL-212/302

---

**6.2.2.** Estimands for 'Percent reduction of mean sUA as computed by subtracting the Baseline sUA level from the mean sUA during Treatment Period 6'

The main estimand for the key secondary efficacy endpoint 'Percent reduction of mean sUA as computed by subtracting the Baseline sUA level from the mean sUA (area under the sUA time curve) during Treatment Period 6' is defined as follows:

- Population: Of all patients with gout refractory to conventional treatment defined by the study inclusion / exclusion criteria, the analysis population will include patients who were randomized to study treatment and who were dosed (ITT population)
- Variable: Continuous variable showing the percentage difference between the mean sUA value recorded in TP6 and the baseline sUA value for each individual, i.e. the  $(\text{mean TP6 sUA value} - \text{baseline sUA value}) \div \text{baseline sUA value} \times 100$ .
- Population-level summary: Difference in LS means between each SEL-212 treatment group vs. placebo.
- Intercurrent events:
  - o All intercurrent events (as listed in 6.1 for the primary estimand) except deaths will be considered using the treatment policy strategy
  - o For deaths the last available value will be used (while-on-treatment strategy), i.e. the baseline sUA value will be subtracted from mean sUA values across the most recently attended TP  $\div \text{baseline sUA value} \times 100$ .

A second estimand for this key secondary endpoint will be defined similarly to the main estimand but with using the while-on-treatment strategy for all intercurrent events (as listed in 6.1 for the primary estimand).

The main and second estimands will be repeated five times, once with the population changed to each of the three defined mITT populations, once with the population changed to the all randomized set, and once with the population changed to the PP set.

**6.2.3.** Estimands for 'The change from Baseline to Day 28 of Treatment Period 6 in the physical summary score of the Short Form Health Survey (SF-36)'

The main estimand for the key secondary efficacy endpoint 'Change from Baseline to Day 28 of TP6 of the Physical Summary Score of the Short Form Health Survey (SF-36)' is defined as follows:

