**Statistical Analysis Plan**  
 Sponsor: Selecta Biosciences  
 Protocol No.: SEL-212/302

---

and percentage of time a patient has sUA values < 6 mg/dL in TP6 will be provided by treatment group in overall and stratified by tophus status at baseline for the ITT.

Summary table of the actual values and change from baseline (Day 0 TP1) for sUA results will be provided for each scheduled sampling time point by treatment group. Additionally, mean sUA level, reduction in mean sUA and percent reduction in mean sUA from baseline during TP6 will be presented by treatment group.

- Mean sUA level is defined as the area under the sUA time curve (computed using the linear trapezoidal rule during Treatment period 6) divided by the corresponding time interval.
- Reduction in mean sUA is computed by subtracting baseline sUA level from mean sUA during Treatment period 6.
- Percent reduction in the mean sUA from baseline is computed as the mean sUA level during Treatment period 6 minus baseline sUA level divided by baseline sUA level multiplied by 100

The sUA levels will be visualized in a box-plot by assessment time and treatment.

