## 12. Deviation from Analyses Planned in Protocol

The key secondary endpoints for gout flare will be analyzed by ANOVA instead of ANCOVA as specified in the protocol, as adjustment for baseline is not possible given gout flare incidence is not assessed at baseline.

Approved

This document is confidential.

SAP Version: 1.1, 22 Feb 2023  
Filing requirements: TMF

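### The fallback analysis of key secondary endpoint 2 takes the log of a signed percent change, which does not exist for any patient whose sUA fell or was unchanged

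*SAP*

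**What the plan says.** SAP 6.2.2 defines the variable for endpoint 2 as a "Continuous variable showing the percentage difference between the mean sUA value recorded in TP6 and the baseline sUA value for each individual", with baseline subtracted from the TP6 mean, divided by baseline and multiplied by 100. SAP 9.1 uses the same sign: "Percent reduction in the mean sUA from baseline is computed as the mean sUA level during Treatment period 6 minus baseline sUA level", over baseline. Protocol 13.4.1 agrees. A fall is therefore negative and no change is zero. The population-level summary in SAP 6.2.2 is a difference in LS means on this scale.

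SAP 9.3.2.2 makes this percentage change the dependent variable of an ANCOVA with treatment, randomization stratum and baseline sUA. It then has the residuals checked for normality and states: "Differences from normality in these residuals will result in the dependent variable being log-transformed and the ANCOVA applied to this outcome". On the status of the log model it says: "This model will then be considered the primary analysis for this estimand". It names no test, threshold or graphical criterion for the check, and no rule for values at or below zero.

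Protocol 13.4.2 has endpoints 1, 2, 8 and 9 "tested between each SEL-212 treatment group versus placebo using an ANCOVA, adjusting for treatment, randomization stratum and baseline value of the respective variable", with no transformation. Protocol 13 says that changes to planned analyses will be identified in the final SAP. SAP 12 lists one: "The key secondary endpoints for gout flare will be analyzed by ANOVA instead of ANCOVA as specified in the protocol". Under SAP 9.3.1 the result for each key secondary endpoint "will be considered as confirmatory, if the p-value of the two-sided test of the previous estimand resulted in a value less or equal 0.025".

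**The concern.** The endpoint is built so that benefit is a negative number, and the fallback takes its log. Followed literally, the analysis has no outcome value for the patients in whom the drug worked. If they are excluded, the arms are compared only among patients whose sUA rose.

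The model whose residuals are checked contains treatment, so the check takes place after unblinding. Any repair devised at that point would be a post hoc choice on a confirmatory endpoint. Because endpoint 2 is second in the fixed sequence, a failed or uncomputable test there also removes confirmatory status from endpoints 3 to 9: SF-36 physical score, tophus response, sUA response in patients with tophi, tender joints, HAQ-DI and both flare endpoints.

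**Working it through.** **The plan's own figures.** The documents give no power or sample size for endpoint 2. The only such figure is for the primary endpoint (SAP 3.5): 45% versus 5%, two-sided alpha 0.025, 90% power, continuity-corrected chi-square. That reproduces as 32 per arm, and 32 / 0.92 = 34.8, so 35 after 8% early termination. The same section gives 47 per arm and a lower active rate of 37%. These rates are used below.

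**Where the log exists.** With an illustrative baseline of 8.0 mg/dL:

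| TP6 mean (mg/dL) | Percent change | Log of percent change | Log with sign flipped | Log(TP6/baseline) |
|---|---|---|---|---|
| 1.0 | -87.5 | none | 4.47 | -2.079 |
| 4.0 | -50 | none | 3.91 | -0.693 |
| 7.9 | -1.25 | none | 0.22 | -0.013 |
| 8.0 | 0 | none | none | 0 |
| 9.0 | +12.5 | 2.53 | none | +0.118 |

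**Responders.** A responder is below 6 mg/dL for at least 80% of TP6. With a baseline of 7 mg/dL, the TP6 mean fails to fall only if the other 20% of the time averages above (7 - 0.8 x 6) / 0.2 = 11 mg/dL. In practice every responder has a negative value and no log.

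**Share of patients without a value.** Let r be the response rate in an arm and f the share of non-responders with a fall or no change (f is an assumption). With equal arms the overall share is the average over arms of r + (1 - r)f.

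- At 45%/45%/5% this is (0.95 + 2.05f) / 3: 32% at f = 0 (about 45 of 141 patients), then 49%, 66% and 83% at f = 0.25, 0.50 and 0.75. It exceeds one half when f is above 0.55 / 2.05 = 27%.
- At 37%/37%/5% this is (0.79 + 2.21f) / 3: 26% at f = 0 (37 of 141), then 45%, 63% and 82%. It exceeds one half when f is above 0.71 / 2.21 = 32%.

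**Flipping the sign.** The patients lost are then those whose sUA did not fall, a share (1 - r)(1 - f) of each arm. At the 45% rate and f = 0.25, 0.50 and 0.75, this is 41%, 28% and 14% on SEL-212 against 71%, 48% and 24% on placebo. This is again selection by outcome, and unequal between arms.

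**Would the switch be triggered?** In SAP 6.2.2, "All intercurrent events (as listed in 6.1 for the primary estimand) except deaths will be considered using the treatment policy strategy". Patients withdrawn under the stopping rule therefore stay in the analysis, and each SEL-212 arm mixes large falls with little change.

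**Simulation.** There were 24 scenarios of 2,000 trials each, with 47 per arm, 60% with tophi, no missing data and SEL-212A compared with placebo. The following inputs are assumptions, because the documents give no distributions:

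- baseline sUA mean 8.7, SD 1.3 mg/dL;
- responders' TP6 mean 1 or 3 mg/dL, SD half the mean;
- non-responders' change, the same in all arms: mean +0.8, +0.4, 0, -0.4 or -0.8 with SD 1 mg/dL, or mean 0 with SD 2 (f about 21% to 79%).

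Shapiro-Wilk, Lilliefors and Anderson-Darling tests at 5% each flagged the residuals in at least 65% of trials in 22 scenarios, and in 20-52% in the other two. Trials favouring SEL-212A at p <= 0.025:

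| Analysis | 45% response | 37% response |
|---|---|---|
| Untransformed ANCOVA | 91-99% | 76-93% |
| Sign-flipped log, falls only | 73-91% | 53-76% |

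The log model as written, on patients with a rise only, did so in 0.7-2.0% over all scenarios. Chance alone in that direction is 0.025 / 2 = 1.25%.

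**The case against.** The lost gate depends on one reading, in which undefined values are dropped and the test is run on the rest. SAP 9.3.2.2 does not say this, and a log that fails for every responder would be noticed. The endpoint's title speaks of a reduction, which lends some support to a sign flip, and then the gate usually passes. If the authors meant the log of TP6 mean over baseline, nobody is lost; a smaller run (600 trials per scenario) gave 88-99% and 73-92% at the two response rates. This stands as a limit on the consequence. It does not rescue the text, which supports neither repair by rule and leaves the choice until after unblinding.

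The near-chance result is partly built in, because non-responders were given the same change in every arm. That is correct. With an assumed extra fall of 0.75 mg/dL in SEL-212 non-responders, the log model on the remaining patients succeeded in about 3-26% of trials, against 95-100% untransformed. The loss is still severe.

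The 7 mg/dL minimum in Protocol 8.1 applies at screening, while baseline is the last pre-dose value (SAP 7.2). At a baseline of 6.5 the 11 mg/dL bound becomes (6.5 - 4.8) / 0.2 = 8.5. The bound is therefore an illustration; the log fails for any fall, whatever the baseline.

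The trigger rates use formal tests that the SAP does not name, and a visual check would fit its wording equally well. They show that the switch is likely, not that it is certain.

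On SAP 12, the log model is still an ANCOVA and method details were left to the SAP. The omission is a documentation point and carries little weight.

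**Conclusion.** The concern holds. That the log is undefined for a fall or no change is arithmetic and needs no assumption, and the SAP makes that model the primary analysis of a gatekeeping endpoint once the residuals look non-normal. The rule gives no value for roughly 26-32% of patients from responders alone, and for about half to four fifths (45-83%) if a quarter to three quarters of non-responders also show a fall.

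If the switch is triggered and undefined values are excluded, endpoints 3 to 9 would very likely lose confirmatory status. That statement rests on the exclusion reading and on the assumed distributions. The harm is lost power and selection of patients by outcome; no inflation of type I error is claimed. A logged outcome would also no longer estimate the difference in LS means of percent change set out in SAP 6.2.2. The primary endpoint and key secondary endpoint 1 are unaffected.

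**What to change.** Delete the residual-triggered switch from SAP 9.3.2.2 and keep the untransformed ANCOVA as the single confirmatory analysis of endpoint 2, as in Protocol 13.4.2. Robust standard errors or a stratified rank test can be added as sensitivity analyses if non-normality is a worry.

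If a log scale is preferred, specify log(mean TP6 sUA / baseline sUA) unconditionally before unblinding, with a rule for values below quantification. In that case restate the summary in SAP 6.2.2 as a ratio of geometric means and list the change in SAP 12.

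Either option needs no new data. The first costs one paragraph of SAP text; the second also changes the estimand summary.
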